### **2.5.6 Clinical Experience**

This is the first clinical study on the safety and efficacy of CB-103 oral capsules for the treatment of patients with locally advanced or metastatic solid tumour and haematological malignancies to date.

As of 20 August 2020, 41 patients (median age 55 years, range 25 to 76 years) with solid tumours have been treated with CB-103 in the dose escalation part of the clinical study at oral doses of 15 mg-600 mg QD. Preliminary safety data indicates that CB-103 is well tolerated with 73.3% of adverse events (AEs) being mild (Grade 1) or 21% moderate (Grade 2) in severity, and 5.7% Grade 3. All AEs were evenly distributed over the dose cohorts with no evidence of dose relation. Cumulatively, a total of 352 AEs has occurred in 41 patients since study initiation, of which 132 AEs (37.2%) in 31 patients were considered related to the study drug. The treatment-related treatment-emergent AEs (TEAEs) most commonly reported ( $\geq 10\%$  of patients) were nausea (24%), diarrhea (20%), dyspepsia (15%), fatigue (12%), and vision blurred (12%).

The majority of treatment-related TEAEs resolved or were resolving at the time of data cut-off without requiring medications or discontinuation of CB-103 dosing. The study includes intense ECG monitoring. There was one related AE of tachycardia Grade 1 (in cohort 2; 30mg QD). Overall, there was no signal of cardiotoxicity and no QTc prolongations have been reported to date.

No events of skin phototoxicity or eye mydriasis have been reported to date in this study. Of the 352 AEs reported, 12 (3.4%) were considered serious adverse events (SAEs) and included abdominal pain, anorexia, atrial flutter, cardiac failure congestive, drug-induced liver injury, duodenal haemorrhage, dyspnoea, general physical condition decreased, respiratory tract infection, spinal cord compression, transaminase increase, and tumour pain. Of these, one SAE was considered related to study drug (drug-induced liver injury), which was reported in a patient with metastatic adenoid cystic carcinoma with extensive liver involvement, treated at an intermediate dose level.

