#### Part A – Dose escalation (Phase I)

Part A will be a dose-finding study based on a 2-parameter BLRM to investigate the safety and tolerability of sequentially enrolled dose cohorts of at least 3, up to 6 patients per dose cohort. Depending on the BLRM, additional patients may be enrolled in some dose cohorts. The first two patients of each dose level will be enrolled in a staggered approach with at least 1 day apart between first dosing of these patients. Subsequent patients may be enrolled concurrently, with at least 1 day apart from the second patient, whereby a dose cohort must be completed with regards to the DLT assessment period and be reviewed by the Cohort Review Committee (CRC) established for this study before further patients are dosed in the next dose cohort. The BLRM will be assessed for those patients satisfying the requirements for inclusion in the dose-determining set (DDS). After completion of a given dose cohort, or at any time the BLRM is updated, the decision to dose escalate and the actual dose and schedule chosen will depend on the recommendation of the BLRM about the highest admissible dose according to the EWOC principle and medical review of available clinical, pharmacokinetic and laboratory data. The outcome of these analyses and the respective datasets will be reviewed by the CRC consisting of the Investigators, Sponsor and CRO representatives, and independent functional experts as required. The CRC will make the decision to determine the next dose level and schedule for the next dose cohort.

Any dose level cohort that has been declared safe after the DLT period, may be expanded by individual patients in order to collect additional pharmacodynamic (PD) and pharmacokinetic (PK) information to support and/or confirm the mechanism of action and explore doses at the currently tolerated dose level or below. These patients will be counted for the respective cohort at the future CRC meetings and will contribute towards the overall safety, PK, PD and clinical efficacy evaluation.

When the MTD/RP2D is defined, based on the decision of the CRC, approximately 45 additional NOTCH-positive patients with recurrent/metastatic ACC, breast cancer, r/r T-ALL/T-LBL, or any other solid tumour with proven Notch pathway activation will receive the MTD/RP2D dose to

[figure not shown]

ascertain that optimal safety related to efficacy and pharmacodynamics in the tumour and in peripheral blood are achieved.

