## 5. Statistical Methods

### 5.1 General Principles

All data processing, summarization and analyses will be performed using Labcorp Drug Development's SAS Environment / Version 9.4 (or later) of the SAS® statistical software package. Baseline, safety and tolerability as well as efficacy analyses will be based on the SS.

Pharmacokinetic evaluation will be done for the PK set.

The dose-determining analyses, i.e. those to determine MTD or RP2D, will be done for the DDS.

Results will be listed and summarized using descriptive statistics overall and by cohort:

- All patients
- Cohort 1 (dosing level 1, e.g. 15mg)
- Cohort 2 (dosing level 2, e.g. 30mg)
- Etc.
- Cohort with RP2D

All summary statistics will be rounded (using the SAS® function ROUND) and presented to one more decimal place than the raw value, except for the minimum and maximum values that will be presented with the same decimal precision as the raw value.

For qualitative variables, the number (n) and percentage (%) of subjects with non-missing data per category will be the default summary presentation, and where appropriate and present, the number of missing values as a "Missing" category. Number of subjects in the analysis population will be used as denominator for percentages calculation, unless stated otherwise in TFLs mock shell(s).

When appropriate, considering number of patients within groups, Clopper-Pearson confidence intervals (CI) will be provided for rates.

For time to event type data, Kaplan-Meier estimates will be presented for dose groups with sufficiently high patient numbers.

Due to being of non-comparative nature, no inferential statistical analysis will be applied in either the escalation or the expansion part of this study to compare dose groups or arms.

The final statistical analysis will occur after all patients have discontinued treatment for any reason and completed safety FU.

All additional data collected during long-term survival FU will be separately reported in a combined FU analysis.

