## **5.4 Demographic and Other Baseline Characteristics**

### **5.4.1 Demographic Characteristics**

All demographic and baseline characteristics will be summarized by cohort for both SS and PK populations and listed accordingly. The summary will include age, gender, race, height, baseline bodyweight, baseline BMI and screening and baseline ECOG. If two populations are identical, the table will be appropriately identified as representing both populations and will not be duplicated. Demographic characteristics will be also provided by subtype of cancer (solid tumours except T-ALL/T-LBL, Adenoid Cystic Carcinoma, T-ALL or T-LBL).

Patients' initial cancer history will be summarized, including tumour type (for breast cancer including ER, PR and HER2 status), Notch status as well as histological tumour grade of initial cancer, also whether or not previous systemic anti-cancer treatments, previous radiotherapies or previous surgeries had been applied and if cancer is recurrent or metastatic; the full information on primary cancer will be provided in Listings.

Active medical history (i.e. histories marked as ongoing at time of screening) will be summarized by number of active disease events, number and percentage of patients with at least one active

disease and number and percentage of patients with each disease displayed by System Organ Class (SOC) and preferred term (PT).

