### 5.6.2 Efficacy Analysis

All efficacy endpoints will be summarized within cohort by descriptive statistics based on SS.

Tumour assessments (via CT, MRI or PET-CT, bone marrow, respectively, pending on tumour type) are scheduled for following time-points:

- At baseline
- During Cycle 2, 4, 6, etc.: on Day 15 (i.e. every 8 weeks)
- At EOT visit

Progression-free Survival (PFS) is assessed explicitly at week 24 and at EOT visit, though disease progression can be detected and recorded at any time-point.

Efficacy parameters are:

- Overall Response Rate (ORR)
- Best Overall Response (BOR)
- Time to Response (TTR)
- Duration of Response (DOR)
- Clinical Benefit Rate (CBR) at 3 months, at 6 months and at 9 months
- Progression-free Survival (PFS)
- Overall Survival (OS)

No formal hypothesis testing is planned.

All lesion and other tumour assessments will be included in the assessment of efficacy parameters.

All efficacy parameters from either the eCRF or calculated as part of statistical analysis will be listed.

In case of patients with solid tumour cancers, baseline lesion status as well as post-baseline assessments of target, non-target and new lesions will be provided. The overall response assessment as of RECIST1.1 are listed by individual cycles.

In T-ALL/T-LBL patients, baseline lesion status, tissue sites involved at baseline, post-baseline lesion status and new lesions will be listed; and so will the overall response assessments by cycle based on NCCN Guidelines on Adult Acute Lymphoblastic Leukaemia.

Patients who cannot be evaluated for response will be categorized as Not Evaluable (NE) or Unknown/Not Assessed (NA).

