### 5.6.2.3 Time to response (TTR) and Duration of response (DOR)

TTR is defined as the time from the first day of study treatment to the first date the response criteria are met, given they were later confirmed. Patients who are not confirmed responders will be censored at the time of their last evaluable tumour assessment. Patients with no tumour assessment after the baseline visit will be censored at the time of the first day of study treatment plus 1 day.

For each dose group, estimates of the median TTR and the corresponding two-sided 95% CI will be presented along with the estimates for the 25th and 75th percentiles and the associated ranges (minimum, maximum) using the Kaplan-Meier (KM) approach.

DOR is defined only for the patients with a confirmed response according to RECIST, v1.1 for patients with solid tumours, according to NCCN guidelines for patients with haematologic malignancies.

By definition, DOR is the time interval between the date of the earliest qualifying response and the date of PD or death from any cause, whichever occurs first. For patients who are alive without progression following the qualifying response, DOR will be censored on the date of last evaluable tumour assessment or last FU for PD before the data cutoff date. Data for patients who are lost to FU prior to documented progression will be censored at the last tumour assessment date which the patient is known to be progression-free prior to the data cutoff date.

For each cohort, estimates of the median DOR and the corresponding two-sided 95% CI will be presented along with the estimates for the 25th and 75th percentiles and the associated ranges (minimum, maximum) using the Kaplan-Meier (KM) approach.

Both TTR and DOR will be provided in Listing.

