#### **5.6.2.5 Progression Free Survival (PFS) and Overall Survival (OS)**

PFS, measured in days, is defined as the time from the first day of study treatment until the first documented progression of disease or death from any cause, whichever occurs first.

PFS for patients who have neither progressed nor died will be censored on the date of last evaluable tumour assessment prior to the data cut-off date. For patients who have not died and have no recorded post-BL tumour assessment, PFS will be censored on the date of the first dose of study medication plus 1 day. Patients who die without any recorded post-baseline tumour assessment after receiving the first dose will be considered to have an event on the date of death. Data for patients who are lost to FU prior to documented progression will be censored at the last evaluable tumour assessments date which the patient is known to be progression-free prior to the data cut-off date.

For each dose group with at least 6 patients, estimates of the median PFS and the corresponding two-sided 95% CI will be presented along with the estimates for the 25th and 75th percentiles and the associated ranges (minimum, maximum) using the Kaplan-Meier (KM) approach.

OS is defined as time between the first day of study treatment and date of death of any cause. Patients for whom no death is captured on the clinical database are censored at the last date they were known to be alive. Patients with no post-BL information will be censored at the time of first study treatment plus 1 day.

For each dose group at least 6 patients, estimates of the median OS and the corresponding two-sided 95% CI will be presented along with the estimates for the 25th and 75th percentiles and the associated ranges (minimum, maximum) using the Kaplan-Meier (KM) approach.

Both PFS and OS details will be provided in Listing.

Futher survival status information from long-term FU will be listed in Listing.

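### The Part A SAP summarises time to response, duration of response, PFS and OS by dose group only, so the RP2D and all-patient curves would mix T-ALL/T-LBL with solid tumours

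*SAP*

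**What the plan says.** SAP Section 5.1 reports all patients together, each dose cohort, and a cohort at the RP2D: "Results will be listed and summarized using descriptive statistics overall and by cohort". For time-to-event data it adds: "Kaplan-Meier estimates will be presented for dose groups with sufficiently high patient numbers". Section 5.6.2 repeats the unit for efficacy: "All efficacy endpoints will be summarized within cohort by descriptive statistics based on SS".

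The endpoint sections follow this. On TTR, Section 5.6.2.3 says: "For each dose group, estimates of the median TTR and the corresponding two-sided 95% CI will be presented". DOR is given per cohort, and its definition covers both RECIST responders and NCCN responders. On PFS, Section 5.6.2.5 says: "For each dose group with at least 6 patients, estimates of the median PFS"; OS is handled the same way. None of the four names a disease stratum.

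Elsewhere the SAP does separate diseases. Section 5.4.1: "Demographic characteristics will be also provided by subtype of cancer (solid tumours except T-ALL/T-LBL, Adenoid Cystic Carcinoma, T-ALL or T-LBL". Best overall response is split into solid and haematologic (5.6.2.1), T-ALL/T-LBL response has its own summaries (5.6.2.2), clinical benefit rate is for solid tumours only (5.6.2.4), and PK is given by indication (5.8.1).

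On who enters where, SAP Section 2.1.1 describes the confirmatory cohort at the MTD/RP2D as "approximately 45 additional NOTCH-positive patients with recurrent/metastatic ACC, breast cancer, r/r T-ALL/T-LBL". Further solid tumours qualify if their Notch activation has been shown. The section sets no quota by disease. For escalation, Protocol Section 2.5.6 reports: "41 patients (median age 55 years, range 25 to 76 years) with solid tumours have been treated with CB-103 in the dose escalation part". The cut-off for that figure is 20 August 2020.

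**The concern.** Survival and progression endpoints depend more on the underlying disease than any other efficacy output in this SAP, yet they are the ones left without a disease split. If T-ALL/T-LBL is concentrated at the RP2D, the RP2D median describes neither leukaemia nor solid tumours, and it shifts with whoever happened to be enrolled. The all-patient summary has the same problem.

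Preliminary anti-tumour activity is a secondary objective of Part A. Someone reading the RP2D median beside those of lower doses could take a difference in patients for a difference in drug effect.

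**Working it through.** The documents give no sample size, event count or power for these endpoints, so there is no planned figure to reproduce. The check has two parts.

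**1. Which diseases are in which group.** Protocol Section 6.1.1, criterion 1c, opens dose escalation to solid tumour indications and to other NOTCH-mutated solid cancers, among which it counts lymphoma. Criterion 1d adds relapsed or refractory T-ALL/T-LBL for the confirmatory cohort and Part B. The escalation data to August 2020 (41 patients) are all solid tumours. Protocol Section 6, however, names haematological malignancies in the Part A escalation population, which does not agree with 1c. So T-ALL/T-LBL enters mainly, not provably only, at the RP2D.

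The mixture would combine:
- NCCN-based response with a first marrow assessment on day 29 (SAP Appendix 3, note 24), and
- RECIST 1.1 response with a first scan at 6 weeks (note 21).

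SAP Section 5.6.2 lists one Day 15 schedule for all modalities, including marrow, but Appendix 3 and Protocol Section 5.1.1.1 both put the leukaemia assessment at day 29.

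**2. Illustration of size.** Inputs:
- T-ALL/T-LBL: 25% one-year survival in 28 patients with at least two prior inductions (Protocol Section 2.3.2).
- Solid tumours: median OS 29.6 months in NOTCH1-mutated ACC and 40 months in NOTCH-high breast cancer (Protocol Section 2.2). I add assumed medians of 12 and 18 months, because the cited figures may be too favourable for this trial's patients.
- Share f of T-ALL/T-LBL in the RP2D group: not stated, assumed 0 to 50%.

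With exponential survival in each disease, t in months:
- T-ALL/T-LBL hazard = −ln(0.25)/12 = 0.1155, so median = ln 2/0.1155 = 6.0 months.
- Solid hazard = ln 2/29.6 = 0.02342, or ln 2/12 = 0.0578.
- Pooled S(t) = f·exp(−0.1155t) + (1−f)·exp(−h·t), with h the solid hazard, solved for S(t) = 0.5.

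Check at f = 0.2, h = 0.02342, t = 21.5: 0.2×0.0835 + 0.8×0.6044 = 0.017 + 0.484, about 0.50.

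Pooled median OS (months), with no drug effect anywhere:

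| T-ALL/T-LBL share | Solid median 12 | 18 | 29.6 | 40 |
|---|---|---|---|---|
| 0% | 12.0 | 18.0 | 29.6 | 40.0 |
| 10% | 11.2 | 16.1 | 25.5 | 34.1 |
| 20% | 10.4 | 14.3 | 21.5 | 28.0 |
| 30% | 9.6 | 12.6 | 17.8 | 22.2 |
| 50% | 8.3 | 9.9 | 12.1 | 13.5 |

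At a 20% share the shift is 29.6 − 21.5 = 8.1 months in one case and 12.0 − 10.4 = 1.6 months in the other. In a confirmatory cohort of 45, a 20% share is 9 patients. The six-patient minimum of Section 5.6.2.5 would be met from 6/45 = 13% upward.

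**The case against.** The case on the other side has real substance.

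- **Entry to escalation.** A reader might infer that T-ALL/T-LBL enters only at the RP2D. The documents do not support that. Criterion 1c admits NOTCH-mutated lymphoma, Section 6 names haematological malignancies for escalation, and the 41 patients are those treated by one cut-off date. This stands.
- **Dose comparison.** A reader might infer that the plan will produce a false fall in survival at the RP2D. SAP Section 5.1 rules out inferential comparison of dose groups, and Section 5.6.2 plans no hypothesis test. Case mix could mislead a reader of the medians, but no planned comparison is biased. This stands.
- **Disease-specific activity elsewhere.** Response is already split, individual TTR, DOR, PFS and OS are listed, and swimmers plots are planned. Confirmatory patients who qualify for an expansion arm also count in Part B (Protocol Section 10.9.2), which reports by indication. A reader might infer that choosing Part B indications depends on the missing PFS and OS split. Part B's success criteria are response rates, so that does not follow.
- **Size.** The cited survival sources differ from this trial in line of therapy and time origin. Part A survival follow-up runs for one year after the End-of-Study visit or last cycle, and long-term data are reported separately, so long medians may not be reached in the main analysis.
- **TTR and DOR.** Best response at the 2020 cut-off was stable disease, so few patients may contribute to DOR.
- **Unseen table shells.** Pooling is inferred from the absence of a split; the shells could add one.

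These points limit the consequence. They do not supply the missing split for the four endpoints in the SAP text.

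**Conclusion.** The concern holds as a gap in specification. Followed as written, the SAP yields RP2D and all-patient summaries of TTR, DOR, PFS and OS that combine NCCN-assessed leukaemia with RECIST-assessed solid tumours, and these could differ from lower doses through case mix alone. No error rate, primary endpoint or planned comparison is affected; the damage is to what the descriptive medians mean.

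The size cannot be fixed from the documents. For a 20% share it runs from 1.6 to 8.1 months of median OS as the solid-tumour median goes from 12 to 29.6 months. That rests on exponential survival, an implied T-ALL/T-LBL median of 6.0 months, and a mix nobody has stated. The direction is the same in every case tried. The change is worth making because the disease groups are already defined and the data already collected.

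**What to change.** In SAP Sections 5.6.2.3 and 5.6.2.5, at the RP2D and overall:

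- Add separate TTR, DOR, PFS and OS summaries for solid tumours and for T-ALL/T-LBL, with ACC shown apart where numbers allow. Use the groups of Section 5.4.1 and say whether the solid-tumour group includes ACC.
- Apply the six-patient minimum of Section 5.6.2.5 to each stratum. Extend it to Section 5.6.2.3, which has no such rule now. List smaller strata only.
- Where dose groups appear side by side, show solid tumours separately. The pooled summary may stay if it is labelled as mixed.

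Separately, reconcile Protocol Section 6 with criterion 1c on whether haematological malignancies belong to the escalation population.

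The cost is SAP wording and a few extra tables. Some strata will be small, with imprecise estimates or listings only. The split does not remove a second difference in case mix: confirmatory patients must be NOTCH-positive, while escalation patients need not be. A footnote should say so.

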#### Notes:

- Any duration [days] = end date – onset date + 1
- All data will be listed
- All unscheduled visits will be summarized into one visit as the final visit in summary tables. In case of multiple unscheduled assessments, the first one will be considered in the summary table but will all be listed.

## **5.2 Subject Disposition and Data Sets Analyzed**

The number and percentage of patients who were screened and have signed informed content, but did not receive any treatment, as well as patients receiving study treatment, in each analysis population, those who are ongoing on study treatment and those who discontinued study treatment together with primary reason for discontinuing treatment, those who completed and discontinued the study as well as the reasons for any premature discontinuation from the study will be summarized by cohort i.e. by dose groups in dose escalation part A. Data will be listed accordingly. Inclusion and exclusion criteria will be listed.

## **5.3 Protocol Deviations or Violations**

### **5.3.1 Violation criteria**

Patients who meet any of the following criteria will be listed and presented in the study report:

- Non-compliance with inclusion criteria.
- Non-compliance with exclusion criteria.

### **5.3.2 Protocol deviations**

All important protocol deviations occurring during the study will be reviewed, classified (as major/minor) and approved by sponsor in data review meeting prior to database lock. Minor deviation (e.g. Deviation in visit windows or time slots) may not justify exclusion of the patient. Should additional important protocol deviations, not anticipated at the time of preparing this SAP, be identified during the study, they will be documented in a separate document and included in all relevant protocol deviation reviews and approvals.

